General Anesthesia Protocol: A standardized general anesthesia protocol was administered to all patients. After preoxygenation (100% 4 L/min O2 for 3 min), patients were induced with propofol (1–2 mg/kg), rocuronium (0.8 mg/kg), and fentanyl (0.1 μ g/kg) via intravenous (IV) route at doses calculated according to IBWs. Mask ventilation and tracheal intubation using

either the McGrath MAC (blade size: 4) or C-MAC videolaryngoscopes (blade size: 4) were performed by an experienced anesthesiologist who had previously used both videolaryngoscopes successfully at least two years (more than 200 times). Also, tracheal intubations were performed by both videolaryngoscopes with the blade size 4 and using stylet in endotracheal tubes. End-tidal carbon dioxide (EtCO2) was continuously monitored after intubation. Tidal volume and ventilation rate were adjusted to maintain the EtCO2 partial pressure of arterial blood at 35–45 mmHg. Additional rocuronium was intermittently injected according to need based on Train of Four (TOF; Dräger AG, Lübeck, Germany) values. TOF responses were assessed by ulnar nerve stimulation and adductor muscle response. Additional fentanyl (0.1–0.2 μ g/kg) was titrated for analgesia, as needed, if HR and/or MAP increased by 20% above baseline during surgery. Anesthesia was maintained in both groups by desflurane inhalation in a 0.5 O2 oxygen-air mixture. Desflurane was discontinued with the beginning of skin sutures and fresh gas flow was changed to 4 L/min of oxygen. In patients who did not

experience complications during surgery, sugammadex (IV, 2–4 mg/kg; Bridion®, MSD, Greenville, USA) was then administrated to reverse residual muscle relaxation at the end of surgery.

Randomization: This study was planned as a randomized prospective study. Randomization was performed using MedCalc v. 16 statistical software for Windows (medcalc.com.tr). Eighty patients were randomly allocated to two groups: McGrath (n = 40) and C-MAC (n = 40) (**Figure 1.** Flow diagram). All patients received standard surgical procedures determined by the same team of surgeons with experience in gastroenterology surgery. Patient pneumoperitoneum pressure ranged from 10–12 mmHg and pneumoperitoneum levels ranged from 30–45 degrees. Surgical management of sleeve gastrectomy and gastric bypass surgeries was not changed in any way.

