Postoperative Management: All patients were transferred to the post-anesthesia care unit (PACU) after surgery. Patients were then transferred to the general surgery intensive care unit when they achieved a score of 9 or higher on the Modified Aldrete score (range 0–12; scores of 9 and above indicate that the patient can be discharged from the PACU) [10]. In all patients, postoperative analgesia was achieved using appropriate IV doses of tramadol (0.5–1 mg/kg) and paracetamol (1 gr) at the time of beginning skin sutures [11].

Outcome Measures: Primary outcome measures were time to intubation and incidence for successful intubations. Time to intubation was defined as the time from when the anesthesiologist picked up the videolaryngoscope to when the anesthesiologist successfully placed the endotracheal tube through the vocal cords, which was assessed by the detection of meaningful EtCO2 levels using capnography. Also, time to intubation was recorded by another anesthesiologist, who accompanied to the study. The characteristics of each tracheal intubation were recorded perioperatively for both groups as secondary outcome measures, including the position requirements for successful intubations (the position at which successful intubation was achieved, neutral vs. sniffing position, i.e., head extension and neck flexion), Cormack Lehane grades (laryngeal view during endotracheal intubation with the videolaryngoscope on a grade of 1=full view of the glottis, 2=partial view of the glottis, 3=only epiglottis visible, 4=neither glottis nor epiglottis visible), glottic view (measured as percentage of glottic opening [POGO] scores), ease of intubation, patient hemodynamic responses and adverse events during intubation. POGO scores were measured on a scale of 1-4 (1 = 75-100% glottic opening; 2 =50-75%; 3 = 25-50%; 4 = 0-25%). Ease of intubation was defined on a grade of 1-3 (1 = noexternal manipulation of larynx was required; 2 = external manipulation of larynx was required; 3 = failed intubation on first two attempts). Incidence, attempts and position for successful intubation, Cormack Lehane grades, POGO scores, and ease of intubation were recorded by the anesthesiologist who performed the tracheal intubation.

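### The secondary outcome on head position is labelled a requirement but records only the position in use at success, so it cannot be separated from the operator's choice of starting position

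*Combined protocol and SAP*

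**What the plan says.** All references are to the combined protocol and SAP.

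- **Outcome Measures, the label.** Among the secondary outcomes the plan lists intubation characteristics, "including the position requirements for successful intubations".
- **Outcome Measures, the definition.** The bracket that follows gives the measurement: "the position at which successful intubation was achieved, neutral vs. sniffing position, i.e., head extension and neck flexion".
- **Outcome Measures, who records what.** The list of items entered by the operator includes "Incidence, attempts and position for successful intubation, Cormack Lehane grades, POGO scores". So the operator records position, and the number of attempts is captured too, but not the position at each attempt. A second person is named for one item only: "time to intubation was recorded by another anesthesiologist, who accompanied to the study".
- **General Anesthesia Protocol.** "A standardized general anesthesia protocol was administered to all patients". For the intubation itself, this section fixes the drugs, blade size 4 and the use of a stylet. It does not mention head position.
- **Statistical Analysis.** Categorical variables, which would include position, are compared between groups by a chi-square or Fisher's exact test.

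No section states the head position at the start of the first attempt or provides for recording it. Blinding is not described.

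**The concern.** A position is shown to be required only if the alternative was tried and did not work. The recorded item does not carry that information. A patient placed in sniffing by choice and intubated at once is entered as sniffing. So is a patient who was started in neutral and moved to sniffing within the same attempt because the tube could not be passed. Only the second shows a need.

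Randomization does not repair this. It balances the patients, but the starting position is chosen after allocation by someone holding the device. If starting positions differ by device, the comparison can show a difference in requirement that does not exist. If sniffing is a common start in both arms, a real difference is diluted. The error can go either way, so the result cannot be assumed conservative.

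At stake is the reading of one secondary outcome: whether a difference, or no difference, in recorded position says anything about what each videolaryngoscope needs.

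**Working it through.** **1. The plan's own figure.** The documents give no rate or power for head position. The only calculation is for time to intubation (Sample Size: SD 18 s, difference 12 s, two-sided alpha 0.05, power 80%). It reproduces: n = 2 × [(1.960 + 0.842) × 18/12]² = 35.3, rounded up to 36 per group as stated. It does not bear on this point.

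**2. Which records are ambiguous.**

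| Record | What it shows about need for sniffing |
|---|---|
| Success in neutral | Sniffing was not needed for that success |
| Sniffing, one attempt | Unclear: neutral may never have been tried, or the head may have been moved within the attempt |
| Sniffing, two or more attempts | Unclear: positions at the earlier attempts are not recorded |

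The main gap is the second row. The number of attempts does not close it, because the plan does not define an attempt or link attempts to positions.

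**3. A model for the size.** Let s be the share of an arm started in sniffing and q the share that truly needs sniffing. Assume that everyone started in sniffing succeeds there, and that those started in neutral move to sniffing only if they need it. Then

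recorded sniffing share = s + (1 − s) × q.

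Inputs: 40 per arm (Randomization); Fisher's exact test (Statistical Analysis); two-sided 0.05. All values of s and q are assumptions. Rejection probabilities come from exact enumeration of all outcomes of two binomials with n = 40.

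**4. Equal true need, different starting habits.** With the same q in both arms, the recorded difference is (s₂ − s₁) × (1 − q), although the true difference is zero. One arm is held at s₁ = 10%. Worked example at q = 10% and s₂ = 30%: 0.10 + 0.90 × 0.10 = 19% vs 0.30 + 0.70 × 0.10 = 37%; rejection probability 0.35.

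| Gap in sniffing starts (s₂) | Probability of a false difference, q from 10% to 30% |
|---|---|
| 0 points (10%) | about 0.03 |
| 5 points (15%) | 0.04-0.05 |
| 10 points (20%) | 0.07-0.11 |
| 20 points (30%) | 0.19-0.35 |
| 30 points (40%) | 0.40-0.66 |
| 40 points (50%) | 0.66-0.89 |

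**5. Different true need, same starting habit.** With a common share z started in sniffing, the recorded difference is (1 − z) × (q₂ − q₁). For true need of 10% vs 40%:

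| z | Recorded shares | Power |
|---|---|---|
| 0% | 10% vs 40% | 0.85 |
| 25% | 32.5% vs 55% | 0.46 |
| 50% | 55% vs 70% | 0.21 |
| 100% | 100% vs 100% | 0 |

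A second set of assumed rates gives the same pattern. With need of 20% in both arms and sniffing starts of 20% vs 40%, 50% or 60%, a false difference appears with probability 0.24, 0.51 or 0.78. With need of 20% vs 50%, power falls from 0.75 with no sniffing starts to 0.22 when half of both arms start in sniffing.

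**The case against.** The case on the other side has several sound parts.

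- **Attempts are recorded.** This stands in part. If a failure in neutral was counted as an attempt, that patient's record differs from a first-attempt success in sniffing. The ambiguity is thus narrower than a total absence of information, but it remains for first-attempt sniffing successes, and positions at earlier attempts are unknown.
- **The definition follows the label at once.** This stands. A careful reader can see what was measured, and the documents state no separate objective or hypothesis about position. Much of the defect lies in the word requirement, which is why relabelling is an acceptable remedy.
- **No operator habit is documented.** This stands. A reader might infer that the position result simply reflects the operator's habit. The documents do not show this: they describe no habit, and they require experience with both devices. A false difference needs starting choices that differ by device, and with a gap of 5 points or less the error rate stays at or below 0.05.
- **The gap may be one of reporting.** Possible. The text is a short account in the past tense, and a common starting position may have been used but not written down.

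A reader might also infer that the primary time to intubation is compromised, because the clock starts at pick-up of the device and would include later repositioning. The documents give no basis for an effect in seconds, and such time may fairly count as part of a device's performance. No claim is made about the primary outcomes.

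**Conclusion.** The concern holds as a mismatch between label and measurement. As written, the plan counts a patient started in sniffing by choice as requiring sniffing, and the between-device comparison cannot be separated from the operator's starting choice. That the operator knew the device is inferred from handling it and from the absence of any described blinding.

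The size is conditional. It ranges from no inflation when starting habits are equal to a false-difference probability of 0.66-0.89 at a 40-point gap, and a shared sniffing start can hide a real difference. These figures show what could happen under assumed rates and the simple model above; they do not estimate what did happen. Because this is one secondary outcome outside the sample-size calculation, the point is minor.

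**What to change.** - **Record the start and every change.** Have the second anesthesiologist, who already times the intubation, note the starting head position and each change of position, by attempt.
- **Analyse what the label claims.** Define the outcome as change from the starting position before success (yes/no), and show it by starting position.
- **If that information is not available,** report the present item as position used at successful intubation and draw no conclusion about requirement.
- **If a common starting position was used,** state it. Which position to use, and when to change it, is left to the investigators.

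Cost: one or two extra fields on the record form, with no extra staff, procedures or patients. Relabelling alone needs no new data.

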Also demographic characteristics, comorbidities, and preoperative airway assessment, including each patient's Mallampati score (1–4), thyromental distance (cm), and mouth opening (cm), were recorded one day before surgery. HR, MAP, respiratory rate, and SpO2 were recorded at baseline before anesthesia (T₀), before intubation (T₁), 1 min after intubation (T₂), 2 min after intubation (T₃), 3 min after intubation (T₄), and 5 min after intubation (T₅). In addition, adverse events of tracheal intubation, including dental trauma, blood on blade, cuff burst, laryngospasm, bradycardia (HR < 65 beats/min), and hypoxemia (SpO2 < 90%), were recorded during the 15 min perioperative period. Hoarseness and sore throat were also recorded during the first 24 hours after surgery.

Sample Size: Statistical power analysis was performed based on a pilot study on 14 morbidly obese patients in our institution showing mean time to intubation of 45 ± 18.0 s [standard deviation (SD)] with the McGrath MAC. For power calculations (OpenEpi, Version 3), equal standard deviation for both groups was assumed. To show a difference of 12 s between the two groups and with an alpha of 0.05 and two tailed and a power of 80%, we calculated that a minimum of 36 patients per group should be included in this study. We ultimately included a total of 80 patients to allow for patient drop-out.

27.06.2018

Statistical Analysis:

Data were analyzed using the Statistical Package for the Social Sciences program (SPSS 22.0, IBM). The Kolmogorov-Smirnov normality test was used to test whether quantitative variables showed a normal distribution. As some patient preoperative and anesthetic characteristics were distributed abnormally, nonparametric statistics was used. Quantitative data are presented as mean or standard deviation and categorical data are shown as numbers or percentages. Continuous variables were compared between the groups using a Mann-Whitney U test. Categorical variables were summarized using frequencies and percentages, and were compared between the groups using a Chi-Square test or Fisher's exact test. A repeated measures ANOVA was used to compare hemodynamic data within each group, while an unpaired t-test was used for comparisons between the two groups. Results were evaluated at a 95% confidence interval at a significance level of p < 0.05.

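### Dental injury first noticed after waking has no described route into the data, and a low laryngospasm count from the undefined 15-minute window would say little about the devices

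*Combined protocol and SAP*

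**What the plan says.** Outcome Measures names, among the secondary outcomes, "patient hemodynamic responses and adverse events during intubation". Later in the same section the events are listed. The list opens with "adverse events of tracheal intubation, including dental trauma, blood on blade" and goes on: "cuff burst, laryngospasm, bradycardia (HR < 65 beats/min), and hypoxemia (SpO2 < 90%), were recorded during the 15 min perioperative period". The section then adds: "Hoarseness and sore throat were also recorded during the first 24 hours after surgery". No other adverse-event collection is described.

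General Anesthesia Protocol sets out when patients are relaxed. Before laryngoscopy, "patients were induced with propofol (1–2 mg/kg), rocuronium (0.8 mg/kg), and fentanyl". During surgery, "Additional rocuronium was intermittently injected according to need based on Train of Four". Sugammadex, in patients without complications during surgery, "was then administrated to reverse residual muscle relaxation at the end of surgery".

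Statistical Analysis sends categorical variables, which would include these events, to a chi-square or Fisher's exact comparison between the arms.

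**The concern.** One collection rule covers six events that come to light at different times. Blood on the blade, cuff burst, bradycardia and hypoxemia are seen or measured around intubation, and a short window suits them. Two events fit less well.

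- **Dental trauma.** The harm is caused at laryngoscopy but may be found later. A tooth damaged out of the operator's sight is noticed when the patient wakes, and by then the plan asks only about the throat.
- **Laryngospasm.** It is looked for while a relaxant is on board, and no recording of it is described after reversal and extubation.

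What is at stake is the safety table. A harm of the device could be undercounted. A reader of a low laryngospasm count could not tell whether the devices are safe in this respect, the event is rare, or the window was one in which it was unlikely to be seen. The undefined start and end add to this, since different recorders could apply different windows.

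**Working it through.** **1. The plan's own figure.** The only computed design figure is the sample size. Inputs from Sample Size: difference 12 s, SD 18.0 s, two-sided alpha 0.05, power 80%.

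n per group = 2 × (1.960 + 0.842)² × 18² / 12² = 2 × 7.85 × 2.25 = 35.3, rounded up to 36.

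The stated 36 reproduces. It concerns time to intubation and does not depend on the adverse-event window.

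**2. Where the 15 minutes lie.** The text calls the period perioperative and gives it no anchor. Three things point to intubation: the outcome is named as events during intubation, the list is headed as events of tracheal intubation, and blood on the blade can only be observed around laryngoscopy. By contrast, the post-intubation vital-sign readings in the same section have stated times, at 1, 2, 3 and 5 minutes after intubation. The intubation reading is the natural one, but it is an inference.

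**3. What each collection period covers on that reading.**

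| Event | 15 min window | First 24 h after surgery |
|---|---|---|
| Dental trauma seen by the operator | yes | not needed |
| Dental trauma first noticed awake | no | not listed |
| Laryngospasm around intubation, relaxant given | yes | not applicable |
| Laryngospasm after reversal and extubation | no | not listed |
| Hoarseness, sore throat | not applicable | yes |

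The second and fourth rows have no described route of capture.

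**4. What a zero count would mean.** The documents give no rate for either event, so the true rate p is assumed over a range. With complete ascertainment, P(no events in 80) = (1 − p)^80:

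| Assumed p | P(0 of 80) |
|---|---|
| 0.2% | 85% |
| 0.5% | 67% |
| 1% | 45% |
| 2% | 20% |
| 5% | 1.7% |

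At rates up to about 1%, a zero is unremarkable even under perfect collection. Rarity and non-ascertainment cannot be told apart from the count.

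**5. What the comparison could detect.** For k/40 against 0/40, the two-sided Fisher p-value is 2 × C(40,k) / C(80,k).

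- k = 5: 2 × 658,008 / 24,040,016 = 0.055
- k = 6: 2 × 3,838,380 / 300,500,200 = 0.026

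Six events (15%) in one arm against none in the other are needed for p < 0.05.

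**6. Effect of missed dental injuries.** Suppose each arm misses the same share s and nothing is falsely recorded. The risk ratio is p1(1 − s) / [p2(1 − s)] = p1/p2, unchanged. The risk difference becomes (1 − s)(p1 − p2), which is smaller, and fewer events mean less precision. The documents give no basis for a value of s.

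**The case against.** The outcome is events of intubation, in a comparison of two laryngoscopes, so confining collection to the period when the device is used is defensible. Laryngospasm at emergence follows surgery, a volatile agent and reversal, has causes other than the laryngoscope, and would add noise. For laryngospasm this stands, and extending its recording is optional. It has less force for dental injury, because damage done at laryngoscopy is an event of intubation whenever it is found.

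It is also fair to say that the operator can see dental damage at laryngoscopy, so the loss is limited to injury that is missed then. That stands, as does the point that equal loss in both arms leaves the risk ratio unbiased. Patients remain under care in the PACU and then in intensive care, so the gap is in trial recording, not in attendance.

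A reader might infer that laryngospasm must be zero because every patient is paralysed throughout the window. The documents do not support that. The window has no stated start, so mask ventilation before the relaxant has full effect may fall inside it. Train-of-four monitoring is described only for top-up doses, and no train-of-four criterion before laryngoscopy is stated.

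A reader might also treat the exact upper limit for 0/40, 1 − 0.025^(1/40) = 8.8%, as the size of the problem. That limit describes any zero count in 40 patients. It does not measure what the window misses, and the plan announces no safety claim based on it.

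**Conclusion.** The point holds as a minor one on secondary safety outcomes. Firmly established from the text: the 15-minute period has no defined start or end, dental trauma and laryngospasm are assigned to that period alone, and the 24-hour collection names neither. On the natural intubation reading, dental injury first noticed awake is not captured. Laryngospasm is expected to be rare in the window whichever device is used, so a low or zero count carries little information about the devices.

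The number of dental injuries lost cannot be calculated from the documents. The primary outcomes and the 36 per group are unaffected. Better collection would not make the trial able to compare rare events; it would make the reported counts mean what they appear to mean. The conclusion rests on the inference that the window surrounds intubation and on there being no recording beyond what is described.

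**What to change.** - State the start and end of the 15-minute window relative to intubation, and who records the adverse events.
- Record dental injury at laryngoscopy and again at the existing 24-hour assessment of hoarseness and sore throat.
- Label laryngospasm in tables as observed within the intubation window, and draw no device-safety conclusion from a zero count. Recording it through emergence is optional; if done, report it separately, since those events have other causes.
- If data collection is already complete, report what was actually sought and when, and state the gap as a limitation.

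The cost is one extra form item at an assessment that already takes place, plus wording. The analysis and sample size do not change.

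### Minor efficiency point on a secondary outcome: the devices are compared on heart rate and MAP by an unpaired t-test with no stated use of the T0 value already recorded

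*Combined protocol and SAP*

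**What the plan says.** Outcome Measures lists among the secondary outcomes "ease of intubation, patient hemodynamic responses and adverse events during intubation". The same section states that "HR, MAP, respiratory rate, and SpO2 were recorded at baseline before anesthesia" (T0), again before intubation (T1), and then at 1, 2, 3 and 5 minutes after intubation (T2 to T5).

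Statistical Analysis gives two methods for these data: "A repeated measures ANOVA was used to compare hemodynamic data within each group, while an unpaired t-test was used for comparisons" between the arms. The first is confined to each arm, and the second is the only comparison of McGrath with C-MAC. The threshold is general: "Results were evaluated at a 95% confidence interval at a significance level of p < 0.05".

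The section does not say whether the t-test uses raw values or changes from T0, or which times are compared. It names no covariate, no device-by-time test and no multiplicity rule.

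**The concern.** The secondary outcome is a response, which suggests movement from a reference reading, and that reading is collected on every patient. The repeated measures ANOVAs describe change over time inside one arm and do not compare the devices. The device comparison therefore rests on the t-test alone, and as written the t-test takes no stated account of T0.

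If T0 predicts the later readings, leaving it out gives a wider confidence interval than the same 80 patients could provide. The silence on raw values or changes also leaves a choice open. What is at stake is precision and clarity on one secondary outcome. The two primary outcomes and the sample size are not affected.

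**Working it through.** **Plan's own figure.** The only sample size calculation is for time to intubation: difference 12 s, SD 18 s, two-sided 0.05, power 80%. n per arm = 2 × (1.960 + 0.842)² × 18² / 12² = 35.3, rounded up to 36. The stated 36 reproduces. The documents give no corresponding figure for HR or MAP.

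**Inputs for the check.** From Randomization: 40 per arm. From Statistical Analysis: significance at 0.05, taken as two-sided. Assumed, because the documents are silent: a device difference of 0.5 SD, and a correlation r between T0 and a later reading of 0.3, 0.5 or 0.7, with r = 0 as the worst case.

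**Raw t-test at one time.** The standard error is √(2/40) = 0.2236 SD, so the noncentrality is 0.5/0.2236 = 2.236. With 78 degrees of freedom, power is 59.8% whatever r is.

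**T0-adjusted comparison at one time.** The variance is multiplied by 1 − r², with 77 degrees of freedom. The last column also multiplies it by 1 + 1/76, to allow for chance imbalance in T0.

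| r | SE ratio √(1 − r²) | Power | Power with imbalance factor |
|---|---|---|---|
| 0 | 1.000 | 59.8% | 59.2% |
| 0.3 | 0.954 | 63.9% | 63.3% |
| 0.5 | 0.866 | 72.2% | 71.7% |
| 0.7 | 0.714 | 87.1% | 86.7% |

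The SE reductions are 5%, 13% and 29%. A simulation of 20,000 trials gave ratios of 0.96, 0.87 and 0.72. The equivalent sample size per arm, 40/(1 − r²), is 44, 53 and 78.

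**Break-even.** (1 − r²) × 77/76 = 1 gives r² = 1/77, so r ≈ 0.11.

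**If the t-test is on change from T0.** The variance is 2(1 − r) = 1.4, 1.0 and 0.6, and power is 46%, 60% and 81%. The excess over the adjusted variance is 2(1 − r) − (1 − r²) = (1 − r)², which is positive for any r below 1. Adjustment therefore does better on this reading too at the three correlations (64%, 72%, 87%).

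**Why a single T2-T5 average is not put forward as the main result.** Suppose the devices differ by 0.5 SD at 1 minute only. The average difference is then 0.5/4 = 0.125 SD.

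- If all readings share one correlation r, the adjusted variance of the average is (1 + 3r)/4 − r² = 0.385, 0.375 and 0.285 at r = 0.3, 0.5 and 0.7. Power is 14%, 15% and 18%.
- In a more cautious case, later readings correlate 0.7 to 0.9 with each other and 0.3 to 0.5 with T0. Power is 9-12%, or 5-7% at 0.025, the first Holm step over two variables.
- A plain t-test at T2 has 60% power for the same difference, and the T0-adjusted difference at T2 has 64%, 72% and 87%.

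**Price of a Holm correction.** Take a sustained difference and a T0 correlation of 0.3. The adjusted average at 0.025 has 66% power (later readings correlated 0.7) or 57% (0.9). The unadjusted average at the plan's 0.05 has 71% or 63%.

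**The case against.** The strongest reply is that nothing is wrong. An unpaired t-test between randomised arms is valid on raw values or on changes, the outcome is secondary, and preferring a covariate-adjusted model is a matter of efficiency. That stands, and it fixes the grade of this point. It does not remove the point, because the adjustment uses data already collected and costs almost nothing if T0 proves uninformative.

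A second reply is that the gain is assumed. That also stands. The documents give no correlation, no haemodynamic SD and no target difference. T0 precedes anaesthesia while T2 to T5 follow intubation, so the correlation may be modest.

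Three stronger readings are tempting and are not supported:

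- A reader might infer that the device comparison is biased or invalid. Randomisation rules that out.
- A reader might infer an inflated false-positive rate from repeated t-tests. HR and MAP at T2 to T5 would make eight tests, and simulation puts the chance of at least one false positive at about 17-32%, depending on the correlations. The plan does not state eight tests, so this is illustrative only.
- A reader might take the anaesthetic protocol's trigger for extra fentanyl, "if HR and/or MAP increased by 20% above baseline during surgery", as showing that the analysis was meant to be relative to baseline. It is a treatment rule during surgery, not an analysis definition.

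**Conclusion.** The point holds as a minor, optional improvement. The plan states no use of T0 when comparing the devices on HR and MAP, and a T0-adjusted comparison would be more precise from the same patients if the T0 correlation exceeds about 0.11. The size, a 5-29% smaller standard error and power rising from 60% to between 63% and 87% at a single time, rests on assumed correlations of 0.3 to 0.7 and an assumed difference of 0.5 SD. The worst case, at zero correlation, is a fall from 59.8% to 59.2%.

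The conclusion does not extend to requiring a T2-T5 average or a multiplicity correction. Each is a trade-off: the average is weak for a brief difference, and Holm lowers power relative to the plan's 0.05.

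**What to change.** For HR and for MAP, replace the between-group t-test with a T0-adjusted comparison. This can be an ANCOVA at each time, or one mixed model of T2 to T5 with device, time, device-by-time and T0. Report the T0-adjusted device difference with its 95% CI at each of T2, T3, T4 and T5, together with the device-by-time test. The differences at each time are needed alongside that test, because a constant difference between devices would not show as an interaction. State that the within-group ANOVAs are descriptive.

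A T2-T5 average and a Holm correction may be added if the authors want a single summary or formal error control, with the limits above stated.

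The cost is a change of analysis wording and slightly more analysis work. The Statistical Analysis text is in the past tense and already comments on the distribution of some variables, so the data may have been examined. If they have, the T0-adjusted analysis should be labelled post hoc and shown beside the t-test.
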